12.3.9.4 Pharmacokinetics

All the PK samples in the trial are trough samples. The trough concentration (C_{trough}) will be listed by treatment group and descriptive statistics will be applied.

C_{trough} values from subjects with positive ADA/nAB will be compared to values from subjects with negative ADA/nAB if data permits.

Trial ID: LP0162-1339	Date: 29-Aug-2018	Version: 4.0
		Page 101 of 129

The PK data will be merged with those from other clinical trials with tralokinumab for a population-based meta-analysis. Results of the meta-analysis will be presented in a separate pharmacometrics report outside of the CTR.

12.3.9.5 Anti-drug antibodies

The frequency of ADAs is an additional secondary endpoint included to assess the safety and tolerability (immunogenicity) of tralokinumab in combination with TCS.

ADA status (positive versus negative) at each visit will be summarised by treatment group for the initial treatment and continuation treatment. If considered relevant, descriptive statistics including number of subjects, mean, standard deviation, median, and range of the actual ADA titres by treatment group and visit will be provided. The ADA status across the trial for each subject (positive vs. negative) will also be classified and summarised by treatment group.

The association of ADA status across the trial (positive vs. negative) with AEs/SAEs may be evaluated. In addition, the association of ADA titres (≥ median titre in positive subjects versus < median titre) with AE/SAEs may be evaluated for ADA-positive treated subjects only. The ADA-positive subjects across the trial may also be divided into persistent positive versus transient positive. A subject will be considered as persistent positive if he/she has positive ADA for at least 2 consecutive visits with ADA assessment. Otherwise, the subject will be considered as transient ADA positive. The associations between ADA and AE/SAEs may be summarised for both persistent positive subjects versus transient positives subjects.

For subjects who develop ADA, the IGA score and change in EASI at end of treatment will be listed.

Evaluations of nAB will be conducted on those serum samples that test positive for ADA. The test sample is deemed positive or negative for the presence of nAB to tralokinumab relative to a pre-determined (in assay validation) statistically derived cut point.

All ADA positive subjects with titre information will be listed.

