Panel 2 Schedule of trial procedures: screening and treatment periods (continued)

									Tre	atm	ent p	erio	d							
	Scree	ning			In	itial	trea	tmer	ıt				Coı	ntinu	atio	n tre	atm	ent		Details
Visit	1 ¹	2	3	4	5	6	7	8	9	10	11	12	13	14	15	16	17	18	19	(protocol section)
Week	-6	-2	0	2	4	6	8	10	12	14	16	18	20	22	24	26	28	30	32	
Visit window (days) ²	±3	-3	NA	±3	±3	±3	±3	±3	±3	±3	±3	±3	±3	±3	±3	±3	±3	±3	±3	
Subject assessment of efficacy																				
eDiary training		X																		10.3.2
eDiary completion ⁷			<-=															->		
POEM			X	X	X	X	X		X		X		X				X		X	10.3.2.7
DLQI			X	X	X	X	X		X		X		X				X		X	10.3.2.8
EQ-5D-5L, HADS			X		X		X		X		X		X				X		X	10.3.2.9, 10.3.2.10
Safety assessments																				
Vital signs	X		X ⁶	X ⁶	X ⁶	X	X	X	X	X	X ⁶	X^6	X ⁶	X	X	X	X	X	X	10.4.1
Physical examination	X		X				X				X								X	10.4.2
ECGs	X		X				X				X				X				X	10.4.3
Serum pregnancy test, hepatitis B, C, HIV	X																			10.4.4, 10.4.5
Urine pregnancy test			X		X		X		X		X		X		X		X		X	10.4.4
Serum chemistry, haematology, IgE	X8		X		X		X		X		X		X		X		X		X	10.4.5
Urinalysis	X		X				X				X				X				X	10.4.5
Pharmacokinetics					X						X								X	10.4.6
Anti-drug antibodies			X		X						X								X	10.4.7
Adverse events	X	X	X	X	X	X	X	X	X	X	X	X	X	X	X	X	X	X	X	11, Appendix 1, Appendix 2

¹⁾ For subjects who do not require a wash-out and subjects who only require washout of topical AD treatment (as specified in the exclusion criteria in Section 8.3), visits 1 and 2 will be combined and screening will be reduced to 2 weeks. Hence, these subjects will only attend visit 2 (Week -2) which will include all assessments shown under Week -6. The screening period has a maximum duration of 6 weeks.

²⁾ If the date of a subject visit does not conform to the trial plan, subsequent visits should be planned to maintain the visit schedule relative to randomisation/baseline.

Trial ID: LP0162-1339	Date: 29-Aug-2018	Version: 4.0
		Page 24 of 129

- 3) The informed consent form must be signed prior to performing any protocol-related procedures, including but not limited to screening evaluations and washout of disallowed medications.
- 4) Re-randomisation at Week 16: the treatment during the continuation treatment period will depend on the regimen received in the initial treatment period and on the subject's clinical response at Week 16 (see Section 7.1). Subjects will continue their use of TCS.

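### The AE/SAE association in 12.3.9.5 uses one whole-trial ADA label per subject, so adverse events that occurred before antibodies appeared count as ADA-positive

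*Protocol*

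**What the plan says.** Protocol section 12.3.9.5 plans two summaries of ADA status. One is by visit: "ADA status (positive versus negative) at each visit will be summarised by treatment group for the initial treatment and continuation treatment". The other is by subject: "The ADA status across the trial for each subject (positive vs. negative) will also be classified and summarised by treatment group". The safety association uses the second: "The association of ADA status across the trial (positive vs. negative) with AEs/SAEs may be evaluated". The further optional splits of ADA-positive subjects, by median titre and by persistence, are also made per subject. On persistence: "A subject will be considered as persistent positive if he/she has positive ADA for at least 2 consecutive visits with ADA assessment". Any other positive subject is called transient, so one positive sample is evidently enough to make a subject positive for the trial.

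Section 12.3.9.1 counts as treatment-emergent any AE beginning after the first dose of IMP. Nothing in 12.3.9.5 restricts the AEs to those after antibodies were found.

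On drug levels, section 12.3.9.4 says trough "values from subjects with positive ADA/nAB will be compared to values from subjects with negative ADA/nAB if data permits". It does not say whether status is taken at the visit or over the trial.

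**The concern.** The exposure in the AE comparison is defined by what happens later. A subject negative at Weeks 4 and 16 and first positive at Week 32 has every AE since Day 0 placed in the ADA-positive group. The clearest case is a placebo non-responder, who under section 7.1 moves to tralokinumab at Week 16. If that subject later becomes positive, AEs from the 16 weeks before any tralokinumab are labelled ADA-positive.

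The label also covers unequal lengths of observation. Subjects who transfer to the extension trial after Week 32 need not give the Week 46 sample. Under section 12.3.11 the safety follow-up results come in an addendum, so a first positive at Week 46 could relabel AEs already reported as ADA-negative.

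ADA frequency is an additional secondary safety endpoint (Panel 4). Section 5.5 lists monitoring for clinical consequences of antibodies, such as immune complex disease, among the measures protecting subjects. The AE association bears on that question, and an attenuated result could be falsely reassuring.

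**Working it through.** The ADA sections contain no figure to reproduce, so the check is how far the whole-trial label distorts an assumed effect.

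**Inputs**
- ADA samples: Weeks 0, 4, 16 and 32 (Panel 2); Week 46 and early termination (Panel 3).
- AE window: from first dose. Treatment lasts 32 weeks.
- Assumed: the AE rate is constant (set to 1) before antibodies and is multiplied by RR afterwards. RR = 2 is the main illustration, with 1.5 and 3 as a range.

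**1. Attenuation of the rate over 32 weeks**

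For a subject labelled positive throughout, observed ratio = (weeks before onset + RR × weeks after onset) / 32. The two onsets are midpoints of sampling intervals.

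| Onset | First positive sample | RR = 1.5 | RR = 2 | RR = 3 |
|---|---|---|---|---|
| Week 10 | Week 16 | (10 + 1.5×22)/32 = 1.34 | (10 + 2×22)/32 = 1.69 | (10 + 3×22)/32 = 2.38 |
| Week 24 | Week 32 | (24 + 1.5×8)/32 = 1.13 | (24 + 2×8)/32 = 1.25 | (24 + 3×8)/32 = 1.50 |

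Whatever RR is, the share of the excess that survives is the share of time after onset: 22/32 = 69% or 8/32 = 25%.

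A placebo non-responder cannot form antibodies to tralokinumab given in this trial before Week 16. Even with onset at Week 16 itself, RR = 2 appears as (16 + 2×16)/32 = 1.50.

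**2. Does reporting by period solve it?**

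Section 12.3.9 reports safety separately for initial and continuation treatment. With onset at Week 24 and RR = 2, the initial period gives 16/16 = 1.00 and the continuation period gives (8 + 2×8)/16 = 1.50. Misattributed events remain in both.

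**3. Direction**

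Ever-positive and never-positive subjects were simulated (1,000,000 per scenario). The assumptions were an ADA hazard of 0.003 per week, an AE rate of 0.01 per week, 30% or 50% followed to Week 46, and 0 to 20% leaving early.
- A true rate ratio of 2.0 appeared as about 1.5.
- With no true effect, the rate ratio stayed near 1.0, but the ratio of the proportions with any AE was 1.03 with no early leavers and up to 1.18 with 20%. Subjects followed for longer have more chance of both a positive sample and an AE.
- The simulation gave early leavers no early-termination sample, so the figures with early leavers are likely to be on the high side.

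**4. What an onset rule recovers (RR = 2, treatment period)**
- Counting from the last negative sample: onset at Week 10 gives (6 + 2×22)/28 = 1.79; onset at Week 24 gives (8 + 2×8)/16 = 1.50. The sampling gap still dilutes.
- Counting from the first positive sample: onset at Week 10 gives (2×16)/16 = 2.00 over Weeks 16-32. Onset at Week 24 leaves no ADA-positive time before Week 32.

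The interval between the two samples therefore has to be handled separately.

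**The case against.** The strongest reply is that this matters little. The association is optional and descriptive, and it lies outside the testing hierarchy of section 12.3.4. The endpoint itself, ADA frequency, is unaffected. Status by visit, AE listings and listings of ADA-positive subjects preserve some of the timing. An onset rule is a detail that an analysis plan could supply, and section 12.3.12 foresees an update before unblinding. All of this stands as to weight. It does not remove the point, because the protocol does not leave the exposure open. It names the whole-trial status.

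Three stronger readings are tempting, and the document does not support them.
- *The trough comparison has the same flaw.* Section 12.3.9.4 does not adopt the whole-trial status and specifies no pooling over visits. ADA and PK samples coincide at Weeks 4, 16, 32 and 46, so matching by visit fits its wording. No size can be put on a rule that is not stated.
- *Subjects who leave because of an AE drift into the ADA-negative group.* Panel 3 schedules ADA at early termination and at safety follow-up, and section 8.5 asks subjects who stop IMP to attend both. Someone stopping at Week 10 is due four samples (Weeks 0 and 4, early termination, follow-up), as many as a completer who transfers at Week 32.
- *The bias always runs towards no effect.* That is the expected direction for a rate. The proportion of subjects with any AE can move the other way.

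**Conclusion.** The point holds for the AE/SAE association. Run as worded, it counts events from before antibodies, and for some subjects from before any tralokinumab, as ADA-positive. Under an assumed doubling, the observed 32-week rate ratio falls to 1.69 for onset at Week 10 and to 1.25 for onset at Week 24. On the per-subject scale, unequal follow-up can also create a modest spurious association. The effect sizes, ADA incidence and follow-up shares are all illustrative, since the protocol gives none. The consequence is limited to interpreting immunogenicity and safety. For trough levels there is an ambiguity to clear up, not an error.

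**What to change.** If the AE/SAE association is run, state in 12.3.9.5 or in the analysis plan update, before unblinding, that AEs and person-time are classified by ADA state over time:
- ADA-negative: time up to the last negative sample before the first post-dose positive, all time of never-positive subjects, and all time before first tralokinumab.
- ADA-positive: time from the first post-dose positive sample.
- The interval between those two samples: shown separately, or assigned each way in turn as a sensitivity analysis.

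Report rates per person-time. Because ADA-positive time falls later in the trial, make the comparison within treatment period. Keep the whole-trial status for the frequency endpoint.

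In 12.3.9.4, add one sentence saying that trough levels are compared by the ADA/nAB result of the same visit.

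The cost is wording and simple programming, since all samples and AE dates are already collected. The downsides are fewer ADA-positive events and onset known only to within a sampling interval of 4 to 16 weeks. Subjects first positive at Week 32 contribute ADA-positive time only in safety follow-up.

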Vital signs	X		X	X ⁴	10.4.1
Physical examination	X		X	X ⁴	10.4.2
EGGs	X		X	X ⁴	10.4.3
Urine pregnancy test	X		X	X ⁴	10.4.4
Serum chemistry, haematology, IgE	X		X	X ⁴	10.4.5
Urinalysis	X		X	X^4	10.4.5
Pharmacokinetics	X		X	X^4	10.4.6
Anti-drug antibodies	X		X	X ⁴	10.4.7
Adverse events	X	X	X	X ⁴	11, Appendix 1, Appendix 2

- Subjects will have a final safety follow-up visit 16 weeks after the last dose of IMP (which is also considered end of trial visit), except subjects who enter the long-term extension trial (conducted under a separate protocol [LP0162-1337, ECZTEND]) for whom the end of trial visit will be the last visit in the present trial before transfer to ECZTEND.
- 2) Subjects who permanently discontinue IMP prior to Week 16 will also attend the nominal Week 16 visit (visit 11x).
- 3) Assessments and procedures performed at Week 16 (see Panel 2) are also to be done at an early termination visit.
- 4) Assessments and procedures to be performed at an unscheduled visit are left at the investigator's discretion; except if due to atopic dermatitis flares, then as a minimum IGA, EASI, concomitant medications/procedures, and AEs are to be assessed.
- 5) eDiary includes: Eczema-related Sleep NRS, Worst Daily Pruritus NRS, Average Daily Pruritus NRS, Days of Topical Treatment Use, Patient Global Impression of Bother, and Patient Global Impression of Severity; subjects will complete daily (Week -2 to 32). Subjects who permanently discontinue IMP prior to Week 16 will complete the eDiary daily until the Nominal Week 16 visit.

Abbreviations: DLQI, Dermatology Life Quality Index; EASI, Eczema Area and Severity Index; ECG, electrocardiogram; eDiary, electronic diary; EQ-5D 5L, EuroQoL 5-Dimension Health Questionnaire 5 Level; HADS, Hospital Anxiety and

Trial ID: LP0162-1339	Date: 29-Aug-2018	Version: 4.0
		Page 26 of 129

Depression Scale; IGA, Investigator's Global Assessment; IgE, immunoglobulin E; IMP, investigational medicinal product; NIMP, non-investigational medicinal product; NRS, numeric rating scale; POEM, Patient Oriented Eczema Measure; SCORAD, Scoring Atopic Dermatitis; SFU, safety follow-up; TCS, topical corticosteroid.

5 Introduction and rationale

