Subjects randomised to placebo in the initial treatment period and with a clinical response at Week 16 will continue to receive placebo Q2W in the continuation treatment period.

Subjects randomised to tralokinumab or placebo in the initial treatment period who do not fulfil either of the criteria for clinical response at Week 16 will receive tralokinumab Q2W in the continuation treatment period.

All subjects will stay on the TCS regimen during the continuation treatment period.

Safety follow-up period (Week 32 to Week 46)

Subjects, except those who enter the long-term extension trial (LP0162-1337, ECZTEND, see below), will complete a 14-week off-treatment follow-up period for the assessment of safety, PK, and anti-drug antibodies (ADA).

Long-term extension trial (selected countries)

Eligible subjects may be invited to enter a long-term extension trial conducted under a separate protocol (LP0162-1337, ECZTEND). Subjects who transfer to ECZTEND must have had their last visit in the treatment period (Week 32 under the current protocol).

Trial ID: LP0162-1339	Date: 29-Aug-2018	Version: 4.0
		Page 37 of 129

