7.3 End of trial definition

A subject is considered to have completed the trial if they have completed all periods of the trial including the safety follow-up visit (Week 46). Subjects entering the long-term extension trial (LP0162-1337, ECZTEND) after completion of the end of treatment visit (Week 32) will also be considered as trial completers.

The end of the trial is defined as the date of the last visit of the last subject in the trial globally.

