10.1 Overview

During the trial, there are 20 scheduled site visits at the clinic. The visits and procedures to be carried out at each visit, as well as the intervals between visits, are summarised as trial flow charts in the schedule of procedures (Section 4). Refer to Panel 2 for assessments during screening and treatment, to Panel 3 for assessments during follow-up (including early termination, nominal Week 16 visit [for subjects who permanently discontinue IMP prior to Week 16] and unscheduled visits), and to Section 7 for further details on the trial design.

Assessments/procedures at any trial visit should be performed in the following order:

- PROs.
- Investigator assessments (performed only by adequately trained investigators; the same investigator should preferably perform all the evaluations for a given subject throughout the entire trial period) in the following order:
 - 1. SCORAD component C, then component A and B.
 - 2. IGA.
 - 3. EASI.
 - 4. AD flares
- Safety and laboratory assessments.
- Administration of IMP.
- Dispensing of NIMP (TCS).

Subjects may also need to be seen at unscheduled visits during the course of the trial. The assessments to be performed at an unscheduled visit are left at the investigator's discretion (could include any assessment performed at an early termination visit) (Panel 3), except if the reason is an AD flare in which case IGA, EASI, concomitant medications/procedures, and AEs should be collected (see Section 10.3.1.4).

Subjects participating in the trial will be under careful supervision of a dermatologist or allergist. Investigators must be experienced in treating AD and have documented experience and/or training in use of the assessments required by the protocol and must be either a physician, certified physician's assistant, or advanced registered nurse practitioner. The

Trial ID: LP0162-1339	Date: 29-Aug-2018	Version: 4.0
		Page 63 of 129

investigators performing the assessments must not be involved in the administration of IMP (see Section 9.2.1).

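### Minor: the ADA rule labels an isolated positive last sample 'transient', and the statement that all PK samples are troughs is wrong for the safety follow-up sample

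*Protocol*

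**What the plan says.** **ADA (Section 12.3.9.5).** The split is optional: "The ADA-positive subjects across the trial may also be divided into persistent positive versus transient positive". The rule is "A subject will be considered as persistent positive if he/she has positive ADA for at least 2 consecutive visits with ADA assessment", and then "Otherwise, the subject will be considered as transient ADA positive". There is no third class and no condition on the last sample.

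**ADA sampling (Section 4, Panels 2 and 3).** Samples are scheduled at Weeks 0, 4, 16 and 32 and at the safety follow-up visit (Week 46). Early termination adds one, and unscheduled visits may. Subjects who enter the extension trial "after completion of the end of treatment visit (Week 32) will also be considered as trial completers" (Section 7.3). Panel 3, footnote 1, says of them: "for whom the end of trial visit will be the last visit in the present trial before transfer to ECZTEND". Week 32 can therefore be their last ADA sample.

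**Late exposure (Section 7.1).** Subjects in either arm "who do not fulfil either of the criteria for clinical response at Week 16 will receive tralokinumab Q2W in the continuation treatment period". Section 10.1 states "Assessments/procedures at any trial visit should be performed in the following order" and lists laboratory assessments ahead of IMP administration.

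**PK (Section 12.3.9.4).** "All the PK samples in the trial are trough samples". The section then plans to compare Ctrough between ADA/nAB-positive and ADA/nAB-negative subjects if the data allow, without naming a visit. Panel 2 schedules PK at Weeks 4, 16 and 32. Panel 3 adds the safety follow-up visit and early termination, and allows PK at unscheduled visits. Section 7.1 describes follow-up as off-treatment and gives PK as one of its purposes. Section 7.4 describes the 16 weeks after the last dose as washout of roughly five half-lives.

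**The concern.** (a) 'Transient' implies that the antibodies went away. Under the residual rule it also covers subjects in whom this was never observed: the last available sample is positive, the preceding one is negative or absent, and nothing follows. If the split is produced and then related to AEs and SAEs, as Section 12.3.9.5 allows, the transient group mixes antibodies shown to have disappeared with antibodies of unknown duration.

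(b) A trough is the concentration at the end of a dosing interval. The safety follow-up sample is a washout sample, and its level mainly reflects time since the last dose. If it counts as Ctrough, the comparison by ADA/nAB status can pool concentrations that differ because of timing, not because of antibodies.

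**Working it through.** **(a) Enumeration of ADA patterns**

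Inputs: the two-consecutive-positives rule (Section 12.3.9.5) and the scheduled samples (Panels 2 and 3). Every sequence of positives and negatives with at least one positive was listed. 'Persistent' means two adjacent positives; the rest are 'transient'.

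| Samples | ADA-positive patterns | Persistent | Transient | Transient and ending positive |
|---|---|---|---|---|
| Weeks 0, 4, 16, 32 | 15 | 8 | 7 | 3 (---+, -+-+, +--+) |
| Weeks 0, 4, 16, 32, 46 | 31 | 19 | 12 | 5 (----+, --+-+, -+--+, +---+, +-+-+) |

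Seen from the other side, 8 four-sample patterns end positive: 3 are transient and 5 persistent. Of 16 such five-sample patterns, 5 are transient and 11 persistent.

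These are counts of possible sequences with equal weight, including ones that are positive at Week 0, before exposure. They are not expected shares of subjects.

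**Who is most exposed to this.** A placebo non-responder gets the first tralokinumab dose at Week 16, after that visit's blood sample. If the subject transfers at Week 32 with no later sample, Week 32 is the only scheduled sample after exposure. With all earlier samples negative, the pattern is ---+, and the subject cannot be classed persistent whatever the true course.

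The size of the parent group follows from the planning rates in Section 12.1, which give 15% placebo response on each primary endpoint. Response on either criterion then lies between 15% (full overlap) and 30% (no overlap). Of 123 placebo subjects, 123 × 0.70 = 86 to 123 × 0.85 = 105 would start tralokinumab at Week 16, before withdrawals. The protocol gives neither a transfer rate nor an ADA incidence, so the number affected cannot be derived.

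**(b) Concentration at safety follow-up**

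Inputs: last dose at Week 30 (Section 9.1.3.1), follow-up visit 16 weeks after the last dose (Panel 3, footnote 1), and 16 weeks as about 5 half-lives (Section 7.4). First-order elimination is assumed.

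- Timing: 30 + 16 = Week 46, and 46 − 32 = 14 weeks. This reproduces the protocol's own figures.
- Half-life: h = 16/5 = 3.2 weeks.
- Fraction left at Week 32, two weeks after the last dose: 2^(−2/3.2) = 0.648.
- Fraction left at Week 46: 2^(−16/3.2) = 0.031.
- Week 46 relative to the Week 32 Q2W trough: 2^(−14/3.2) = 0.048, about 5%.
- Range, as Section 7.4 says only 'approximately': 0.065 if 16 weeks is 4.5 half-lives (h = 3.56 weeks), and 0.036 if it is 5.5 (h = 2.91 weeks).

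**The case against.** **On the ADA rule.** The rule is explicit, exhaustive and reproducible, and the split may never be produced. Section 12.3.9.5 also plans ADA status by visit, ADA status across the trial and a listing of positive subjects with titres, so late positives stay visible. Section 12.3.12 provides for a blinded review and an update of the analysis plan before unblinding. All of this stands, and it keeps the point minor. It does not make the label right for an isolated positive last sample.

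A reader might infer that the rule calls every subject with a positive last sample transient. It does not: 5 of 8 such four-sample patterns and 11 of 16 five-sample patterns are already persistent. The weakness is limited to last positives without two consecutive positives anywhere, and it is a weakness of definition, not a contradiction.

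**On PK.** Section 12.3.12 tabulates data by visit, which partly protects the summaries, though not the comparison by ADA/nAB status. Two stronger readings are not supported:

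- A reader might conclude that early-termination and unscheduled samples are never troughs. They have no fixed interval from the last dose, and an early-termination sample taken when the next dose would have been due is a trough. The documents show only that trough timing is not guaranteed.
- A reader might infer that washout samples from subjects who stop IMP early enter the 32-week analysis, because their follow-up visit can fall by Week 32. Section 9.2.1 cuts that analysis at visit 19, whereas safety follow-up is visit 20, and Section 12.3.11 places safety follow-up results in an addendum. Contamination of the 32-week analysis is not established.

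It is also fair that limiting Ctrough to Weeks 4, 16 and 32 does not by itself guarantee troughs, since dosing may be rescheduled (Section 9.1.3.1) or suspended (Section 9.7.2). The fix has to cover this.

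**Conclusion.** Both parts hold in limited form and are minor. Part (a) is a badly fixed definition: an isolated positive last sample is called transient without evidence that the antibodies disappeared. Part (b) is a factual error in the protocol for the safety follow-up sample, and an assurance it cannot give for early-termination and unscheduled samples.

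In size, 3 of 7 or 5 of 12 transient patterns end positive, with the number of subjects unknown. The follow-up concentration is about 5% (3.6% to 6.5%) of the Week 32 Q2W trough, resting on first-order elimination and the protocol's own half-life statement. No confirmatory test and no overall ADA frequency changes; only descriptive ADA and PK outputs do.

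**What to change.** (a) If the split is produced, require a negative last available sample for 'transient'. Class subjects with a positive last available sample who do not meet the persistent rule as 'indeterminate'. No transient pattern then ends positive.

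(b) Delete or correct the sentence that all PK samples are troughs. Restrict Ctrough and its comparison by ADA/nAB status to the scheduled on-treatment samples at Weeks 4, 16 and 32, by visit and treatment group, and exclude or flag samples taken after a missed or suspended dose. Report safety follow-up, early-termination and unscheduled concentrations separately.

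Cost: wording only, as all samples are already collected, plus a small third ADA category and one extra PK table.
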